### Exclusion criteria

- a) Women less than 18 years or older than 45 years
- b) Women who are pregnant at the time of evaluation
- c) Postmenopausal women
- d) Women who had undergone hysterectomy and/or bilateral oophorectomy
- e) Anything that would place the individual at increased risk or preclude the individuals compliance with or completion of the study.
- f) Unwillingness to participate or difficulty understanding the consent process or the study objectives and requirements.

## Study Duration

From when the study opens to enrollment until completion of data analyses – 12 months.

### Subject Participation Duration

Minimum duration – 1 visit

Maximum duration – 12 weeks (3 visits)

Estimated Time to Complete Enrollment:

Approximate duration – 9 -12 months.

### Sampling technique

A consecutive sampling technique will be used for each phase of the study. Consecutive study participants, who meet the selection criteria and give informed written consent, will be recruited for the study. A unique serial identification number will be given to each study participant until the intended sample is attained.

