#### Strategies for Sampling, Recruitment and Retention

Participants will be sampled proportionally from all 8 zones as shown above in Trinidad. Approximately 124 women in the reproductive age (18 – 45 years old) will be randomly sampled from each zone. Houses will be numbered and random numbers of these houses will be generated using random number calculator. In each sampled house, females would be prescreened and those that satisfy our inclusion criteria would be selected. Telephone numbers of participants will be obtained and follow-up calls made.

Sample size calculations were based on the following formula (32):

$$n = [(Z_{1-\alpha})^2(P(1 - P)/D^2)]$$

where n = individual sample size,  $Z_{1-\alpha} = 1.96$  (when  $\alpha = 0.05$ ), P = assumed prevalence, and D = absolute error.

Sampling units are defined as individual unselected women between the ages of 18 and 45 years, identified in the community. We target power analysis on women who do not use hormonal contraception. We assume a conservative response rate of 50% of sampled women. This response rate includes the following parameters:

use of hormone/contraceptive use (15%), excluded due to hysterectomy or ovariectomy (3%), excluded due to pregnancy (2%), refusal to participate (20%), and study drop-out/lost to follow-up (10%).

A conservative prevalence estimate for PCOS based on a review of nine studies conducted in the general population using the Rotterdam 2003 definition is 13.4% (4, 5, 33-39). Using the above formula, a sample size of 495 individuals will be required to determine the prevalence with an absolute error of  $\pm 3\%$ . Assuming a 50% enrollment rate, 990 women would need to be approached for study inclusion.

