## Selection criteria

### Inclusion criteria

- a) Female, ages 18 to 45 years., all ethnic backgrounds.
- b) The participants must have at least one of the following two features:
  - i) Dermatological signs or complains of clinical hyperandrogenism such as unwanted facial or body hair, loss of scalp hair (alopecia) or persistence acne (pimple).
  - ii) Signs or complains of ovulatory dysfunction such as irregular menses (oligomenorrhoea, amenorrhea or polymenorrhoea), history of anovulation or ultrasonographic findings of polycystic ovarian morphology.

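### The plan prescribes both random household sampling and consecutive sampling, and does not say how the two fit together

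*Combined protocol and SAP*

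**What the plan says.** Two sections of the combined protocol and SAP describe how women enter the study.

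- *Strategies for Sampling, Recruitment and Retention* describes a random draw of dwellings: "Houses will be numbered and random numbers of these houses will be generated using random number calculator". It continues: "In each sampled house, females would be prescreened and those that satisfy our inclusion criteria would be selected". On allocation it states "Participants will be sampled proportionally from all 8 zones as shown above in Trinidad", and then gives the number for each zone: "Approximately 124 women in the reproductive age". It does not give the number or fraction of houses to be drawn in a zone.
- *Sampling technique* states "A consecutive sampling technique will be used for each phase of the study". It recruits eligible women who consent, one after another, and closes: "A unique serial identification number will be given to each study participant until the intended sample is attained". It mentions neither houses nor a random draw nor zones. The phases are not defined anywhere.

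The sole primary objective is the prevalence of PCOS in women aged 18 to 45 in Trinidad. The sample size of 495 is set for an absolute error of ±3 points, with 990 women approached at 50% enrolment.

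*Data management and Statistical analysis* does not mention prevalence. Categorical variables are reported as counts and percentages, the only confidence interval named is for the odds ratio, and there is no reference to weights, strata or clusters.

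**The concern.** A random draw of houses with a recorded sampling fraction gives each woman a known chance of selection, and that is what supports a population prevalence with a confidence interval. Consecutive recruitment of whoever is eligible and willing does not. Field staff who followed *Sampling technique* alone would comply with the protocol and yet produce a non-probability sample. The direction and size of any resulting bias could not be determined, and no analysis afterwards could recover the missing probabilities.

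The allocation matters for the same estimate. If zones differ in size and each contributes about 124 women, a pooled unweighted percentage gives women in small zones too much influence. It is then biased for Trinidad when prevalence is related to zone size, and not biased on this account when it is unrelated.

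**Working it through.** **The plan's own figure.** Inputs from *Strategies for Sampling, Recruitment and Retention*: Z = 1.96, P = 0.134, D = 0.03.

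n = Z² × P(1 − P)/D² = 1.96² × 0.134 × 0.866/0.03² = 495.3. The plan's 495 is reproduced, and 495/0.5 = 990. The arithmetic is not in dispute. The formula assumes a simple random sample of independent women.

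Half-width at n = 495: 1.96 × √(0.134 × 0.866/495) = 3.00 points.

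**The two sampling rules side by side.**

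| | Strategies for Sampling, Recruitment and Retention | Sampling technique |
|---|---|---|
| How women are located | Randomly drawn, numbered houses | Not stated |
| Who is taken | Women in the house who meet the criteria | Consecutive eligible, consenting women |
| Zone target | About 124 in each of 8 zones | None |
| Link to the other section | None | None |

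Selection probabilities cannot be obtained from the right-hand column. The left-hand column would supply them only if the houses numbered and drawn in each zone were also recorded.

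**Allocation.** 990/8 = 123.75, so about 124 per zone is an equal split of the women approached (8 × 124 = 992). About 495/8 = 61.9 per zone would be enrolled.

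**Cost of weighting an equal split.** The text available gives no zone sizes, so two sets of shares of women aged 18–45 are assumed:

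- A: 0.18, 0.16, 0.14, 0.13, 0.12, 0.10, 0.09, 0.08
- B: 0.25, 0.20, 0.15, 0.12, 0.10, 0.08, 0.06, 0.04

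With equal numbers per zone, the Kish factor is 8 × Σ(share²).

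- A: 8 × 0.1334 = 1.07; half-width 3.00 × √1.067 = 3.10 points
- B: 8 × 0.1610 = 1.29; half-width 3.00 × √1.288 = 3.41 points

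**Household clustering.** Design effect = 1 + (m − 1) × ICC, with m women per house assumed to be 1.1 to 1.5 and ICC assumed to be 0.1 to 0.5.

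- Lowest: 1 + 0.1 × 0.1 = 1.01; half-width 3.02 points
- Highest: 1 + 0.5 × 0.5 = 1.25; half-width 3.36 points

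**Both together, upper case.** 1.288 × 1.25 = 1.61; half-width 3.00 × √1.61 = 3.81 points.

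**The case against.** The strongest reply is that the two sections do different jobs: one says how women are located, the other how those who qualify and consent are enrolled and numbered. On that reading they run in sequence, the intended sample is the number already set, and a missing zone target in the second section is no conflict because the first supplies it. *Study procedure* invites women from selected geographical locations, which fits choosing places before enrolling. This reading is possible, and it stands as a reason not to call the sampling irreconcilable. It does not remove the problem, because no section states it and *Study procedure* does not mention houses.

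The *Quality assurance* section plans to use the study register to compare participants with non-participants. That addresses refusal among women already identified, not how they came to be identified.

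A reader might infer more than the documents support:

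- **That this is in fact a clinic or convenience sample.** *Study sites* names one faculty, and *Job description* has physicians and nurses identify potential participants. Neither says that women are recruited from a clinic.
- **That the equal split contradicts the word proportionally.** It may not. The zone exhibit to which the section refers was not in the text available for this review, and zones of similar size would make both statements true.
- **That the missing prevalence estimator and interval is an error in itself.** It is missing detail. Plain percentages can cover a crude proportion, and the sample size formula implies a simple interval, although neither is named for prevalence.

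**Conclusion.** The point holds as an unreconciled pair of sampling rules for the sole primary outcome, and it needs correcting before recruitment. If *Sampling technique* is followed in place of the household draw, the ±3 points has no probability basis, and the effect on the estimate cannot be quantified from the documents. If it means only sequential enrolment within drawn houses, the fault is one missing statement.

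The allocation point is conditional on unequal zones. The precision figures (about 3.1 to 3.4 points from weighting alone, about 3.8 in the upper combined case) rest entirely on assumed zone shares, household sizes and ICCs, and serve only to show scale. Household clustering alone is likely to be minor.

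Precision for all women aged 18–45 also depends on a separate conflict. The sampling section says "Sampling units are defined as individual unselected women between the ages of 18 and 45 years, identified in the community", whereas *Inclusion criteria* says "The participants must have at least one of the following two features" and lists symptoms or signs. Until that is reconciled, no weighting makes the estimate refer to all women in the age range.

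**What to change.** 1. In *Sampling technique*, delete the consecutive rule, or restrict it explicitly to enrolling women in sequence within the randomly drawn houses.
2. In *Strategies for Sampling, Recruitment and Retention*, state the number or fraction of houses drawn per zone. Record zone and household for every woman approached.
3. If the zones differ in numbers of women aged 18–45, choose one of two routes. Either allocate the 990 in proportion to zone size, which carries no weighting loss, or keep about 124 per zone and weight by inverse selection probability. That weight is houses numbered over houses drawn in the zone, or approximately zone women aged 18–45 over women sampled (the roughly 124 approached, not the roughly 62 enrolled). State any adjustment for response separately.
4. In *Data management and Statistical analysis*, estimate prevalence and its 95% confidence interval with zone as stratum and household as cluster, instead of a crude percentage.
5. State that ±3 points assumes a design effect of 1, and restate it from the actual zone and household counts.
6. Reconcile the sampling unit with the inclusion criteria, as a separate change.

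The cost is wording in three sections, zone counts of women or houses, two identifiers and a survey-method analysis. The downside is wider stated precision. No extra participants are needed if that is accepted. Holding ±3 points under an equal split could be expensive: with shares B, 495.3 × 1.288 = 638 enrolled and 1,276 approached, before clustering. Restating the precision is the more practical course. The draw fractions and identifiers should be fixed before recruitment because they may not be recoverable later.

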### Study procedure

Potential study participants from selected geographical locations will be invited to participate in the study. A confidential study register (see attached) containing details of potential study participants (name, age, height, weight, blood pressure and contact phone number) will be kept. Potential study participants will be counselled on the objectives of the study and the study protocol. If the potential participant refuses to participate, no further contact will be made with the participant. Informed consent (see attached) will be obtained from each eligible study participant before recruitment for the study. A subject tracking log for longitudinal observation study will be used to track eligible subjects.

After an informed consent, data will be collected from each study participant using a standard format in a clinical report form (CRF) for uniform data collection from all participants. Each CRF will contain a unique serial identification number. The CRF will be filled by a suitably trained researcher (including the PI, co-investigators and medically trained research assistants). All CRFs will be checked for missing data within 24 hours of completion, and any missing data will be detected and collected immediately.

Each participant will undergo anthropometric measurements (weight, height, waist, circumference and hip circumference) and physical examination for hirsutism, acne, alopecia, acanthosis nigricans, and thyroid enlargement. Participants with an initial hirsutism (mFG) score of 3 or more ( $\geq 3$ ) will be re-assessed by a physician.

After overnight fasting (of 8 hours or more), 10 ml of venous blood sample will be collected from each study participant; within the first seven days of spontaneous or induced menstrual cycle. About half (5 ml) of the venous blood will be collected in an EDTA-containing tube for plasma/DNA and the remaining in a plain tube for serum. Aprotinin will be added to plain tubes to prevent breakdown of small proteins that may be useful for measures. Aprotinin is a small protein bovine pancreatic trypsin inhibitor that inhibits trypsin and related proteolytic enzymes. During the mid-luteal phase of the menstrual cycle (between day 20 and 24), 5 ml of venous blood sample will be collected in a plain tube for serum progesterone.

All blood samples will be stored and transported to the laboratory in cooler boxes containing ice packs immediately after collection. At the laboratory, the sample will be separated into serum, plasma and whole blood by centrifugation for 20 minutes at 3000 rpm. The biological specimens will be stored, in small aliquots (of 0.5 ml), in 1.5 to 2.0 ml plastic containers (about 12 cryovials) able to withstand temperatures of -80°C.

Samples for hormonal assay and initial evaluation will be batched at regular interval for analysis to provide study participants with timely results, allow classification of participants, and minimize the impact of inter-assay variability. At the end of the study, a repeat analysis of biological samples for androgen levels and insulin estimation will be performed at a reference laboratory. Each subject will also complete the following standardized data instruments or forms as appropriate: FG Score self-assessment, SF-12, Beck depression inventory, Epworth sleepiness scale, and uterine fibroid assessment (see attached).

We propose to establish collaboration between the University of Lagos and the Laboratory of [name], a world renowned scholar on the subject of PCOS in the United States. The genetic analysis will be performed at the Laboratory at the Department of Pre-clinical Sciences. The initial evaluation and classification of study participants will be done using the flow chart/diagnostic tree by Azzizz et al. (Figure 1).

Related or mimicking disorders will be excluded using history, physical examination, and serum TSH, prolactin and 17-OH progesterone. Participants with hypothyroidism on thyroxine replacement therapy will not be recruited for the study until TSH level is normal. Study participants with elevated 17-OH progesterone > 2ng/dl (or 200 ng/dl) will have non-classical congenital adrenal hyperplasia (NCAH).

A summary of initial and follow-up procedures.

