#### Secondary

2. To determine the distribution of phenotypes among women diagnosed with PCOS in the above objective overall and by ethnicity. PCOS sub phenotypes are as follows: Phenotype A – clinical and/or biochemical hyperandrogenism (HA) and oligi-/anovulation (OA), and polycystic ovarian morphology (PCOM); B – HA and OA; C – HA and PCOM; and D – OA and PCOM;
3. To determine the risks for, metabolic syndrome, depression, obstructive sleep apnea symptoms, fibroids, and general health issues for PCOS women versus women without PCOS in the age groups 18 – 45 years.
4. To determine the genotype of PCOS in Trinidad.

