#### Outcome measures and variables

## Outcome measures (dependent variables)

- a) Primary outcome
  - i) Prevalence of PCOS and its symptoms
- b) Secondary outcome
  - i) Phenotype of PCOS
  - ii) Genotype of PCOS
  - iii) Prevalence and prevalence ratio for PCOS subphenotypes in Trinidad, odds ratio for metabolic syndrome, depression, obstructive sleep apnea symptoms, fibroids, and general patient health issues, adjusted for age, ethnicity, BMI, treatment (OCP), and socioeconomic parameters.

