***Study specific medical examination will include:***

- Waist and hip circumferences measurement
- Hirsutism assessment
- Acne assessment
- Alopecia assessment
- Acanthosis nigricans assessment

Data Collection:

Types of data:

Independent variables

1. Socio-demographic variables
2. Baseline characteristics

Dependent variables

3. Primary outcome
  - I. Prevalence of PCOS
4. Secondary outcome
  - II. Phenotype of PCOS
  - III. Genotype of PCOS
  - IV. Prevalence of obesity
  - V. Prevalence of hirsutism
  - VI. Prevalence of diabetes

Data collection instrument:

The methods of collecting data for assessment of study objectives include the use of standardized interview-based medical forms; surveys; physical examination.

The CRF developed for this study include; clinical and anthropometric section; radiological report section and laboratory result section. The questionnaire section will seek information on socio-demographic variables, reproductive history with emphasis on menstrual cycle (dating and regularity) and gynecological history, hirsutism, acne, medications, and family history. The anthropometry and clinical section will document the physical findings such as hirsutism, acne, alopecia, acanthosis nigricans, and thyroid enlargement. The pelvic ultrasonographic findings will be recorded in the laboratory result section. Subjects will also complete the

following standardized data instruments or forms as appropriate: FG Score self-assessment, SF-12, Beck depression inventory, Epworth sleepiness scale, and uterine fibroid assessment.

Expected duration of subject participation is approximately from 1 to 3 cycles or 12 weeks. Approximate time to complete enrollment is 9 to 12 months. Approximate time to complete study is 18 to 24 months.

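### The outcome called obstructive sleep apnea symptoms has only a sleepiness scale named behind it, so its odds ratio would describe daytime sleepiness

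*Combined protocol and SAP*

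**What the plan says.** Secondary objective 3, under Aims and objectives, is "To determine the risks for, metabolic syndrome, depression, obstructive sleep apnea symptoms, fibroids, and general health issues for PCOS women versus women without PCOS". Under Outcome measures and variables, secondary outcome iii turns this into an effect measure: "odds ratio for metabolic syndrome, depression, obstructive sleep apnea symptoms, fibroids, and general patient health issues". The same item says that these estimates will be "adjusted for age, ethnicity, BMI, treatment (OCP), and socioeconomic parameters". Both statements are repeated later in the document, where the outcome is numbered vi.

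The forms that should supply these outcomes are listed twice. Study procedure gives "FG Score self-assessment, SF-12, Beck depression inventory, Epworth sleepiness scale, and uterine fibroid assessment (see attached". The paragraph on the data collection instrument repeats the same five: "following standardized data instruments or forms as appropriate: FG Score self-assessment, SF-12, Beck depression inventory, Epworth sleepiness scale, and uterine fibroid assessment".

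On the interview, that paragraph says "The questionnaire section will seek information on socio-demographic variables, reproductive history with emphasis on menstrual cycle (dating and regularity) and gynecological history", and goes on to hirsutism, acne, medications and family history. The examination in Study procedure adds anthropometry and "physical examination for hirsutism, acne, alopecia, acanthosis nigricans, and thyroid enlargement".

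The section on data management and statistical analysis names linear and logistic regression. It does not say how any questionnaire score becomes a yes/no outcome.

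**The concern.** The outcome is named after a breathing disorder during sleep. The one sleep instrument in the text is, by its own name, a measure of sleepiness. Sleepiness can accompany obstructive sleep apnea, but it also has other causes.

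Followed as written, the plan would report a sleepiness comparison under an apnea label. A woman who snores and stops breathing at night but is not sleepy would count as unaffected. A woman who is sleepy for another reason would count as affected. A reader of the results could not tell these cases apart, and might take a finding about sleepiness as evidence on apnea in women with PCOS.

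There is also a gap in definition. An odds ratio needs a binary outcome, and the text gives no Epworth threshold.

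**Working it through.** The plan states no figure for the sleep outcome, so the check is mainly a comparison of what is promised with what is measured.

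**1. What is promised.** Objective 3 has five components: metabolic syndrome, depression, obstructive sleep apnea symptoms, fibroids and general health. Secondary outcome iii asks for an adjusted odds ratio for each.

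**2. What is named as a source for the sleep component.**

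| Place in the document | Content named | Bears on sleep or breathing at night? |
|---|---|---|
| Instrument lists (Study procedure; data collection instrument) | FG self-assessment, SF-12, Beck, Epworth, fibroid assessment | Epworth only, as sleepiness |
| CRF questionnaire topics | Socio-demographic, menstrual and gynecological history, hirsutism, acne, medications, family history | None named |
| Examinations | Blood pressure, height, weight, waist and hip, skin and hair signs, thyroid, pelvic and breast exam | None named |
| Table 1 | TSH, prolactin, 17-OHP, progesterone, oGTT | None |
| Table 2 | SHBG, testosterone, DHEAS, DNA, repository blood | None |

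No snoring, witnessed-apnea or choking item, oximetry or sleep study appears in the text.

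**3. How the outcome would be derived.** The statistical section gives no cut-off and no case definition. The dependent-variable list under Data Collection does not mention the sleep outcome, so it supplies no definition either. On the text alone, the only quantity available is the Epworth score, dichotomised at an unstated point.

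**4. Does the primary estimate depend on this?** The plan's formula reproduces its own sample size: 1.96² × 0.134 × 0.866 / 0.03² = 495.3, which matches 495; and 495 / 0.50 = 990, which matches the number to approach. No sleep measure enters this calculation.

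**5. Can the consequence be sized?** Not from the documents, which give neither a frequency of apnea symptoms nor the accuracy of the scale. As an illustration with every input assumed, let p be the true frequency in a group and q the frequency classified as affected:

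q = sensitivity × p + (1 − specificity) × (1 − p)

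- One case: sensitivity 0.5 and specificity 0.7 in both groups, p = 0.10 without PCOS, true odds ratio 2.
- With PCOS, the odds are 2 × 0.10/0.90 = 0.222, so p = 0.182.
- Then q is 0.5 × 0.10 + 0.3 × 0.90 = 0.320 without PCOS, and 0.5 × 0.182 + 0.3 × 0.818 = 0.336 with PCOS.
- The observed odds ratio is (0.336/0.664) / (0.320/0.680) = about 1.08.
- For sensitivity and specificity pairs from (0.4, 0.7) to (0.6, 0.8), and p from 0.05 to 0.20 without PCOS, a true odds ratio of 2 appears as 1.02 to 1.29.

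This covers only the case of equal error in both groups. If sleepiness from other causes differs by PCOS status, the observed value can move either way, so no direction of bias is established.

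**The case against.** **The outcome says symptoms, not diagnosis.** This stands in part. No diagnosis of sleep apnea is promised, and sleepiness can be one of its symptoms, so the scale is relevant. But the label ties the symptom to obstructive apnea, and sleepiness alone cannot carry that attribution. The defect is a broad label on a narrow measure.

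**The forms are attached and unseen.** This also stands. The CRF description is a summary that does not claim to be complete. A reader might infer that no breathing symptom will be recorded at all; the documents do not support going that far. What can be said is that none is named, in two instrument lists and a description of the interview.

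**Depression is missing from the adjustment set.** A reader might infer that this omission is an error and that it inflates the odds ratio. The documents support neither inference. Depression may follow from PCOS or from disturbed sleep, and adjusting for it could then remove part of the difference objective 3 asks about. Leaving it out is defensible. Adjustment would not cure the labelling either, since sleepiness adjusted for the Beck score is still sleepiness.

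**The objective can still largely be addressed.** Correct. The other four components do not use the Epworth scale, and it would be wrong to say that objective 3 as a whole fails.

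**Conclusion.** The point holds as a mismatch between an outcome's name and its measurement. On the text available, the odds ratio labelled obstructive sleep apnea symptoms would be an odds ratio for daytime sleepiness, with the threshold left open. It concerns one of five components of one secondary objective. It does not touch the primary prevalence estimate or the sample size of 495.

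The conclusion rests on two things: that the text's lists reflect what will be collected, which the unseen attachments could change, and that sleepiness is not specific to sleep apnea. It does not rest on the numerical illustration, whose inputs are all assumed. The documents do not show how large the discrepancy would be, or in which direction.

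**What to change.** Choose one of two routes, before data collection if possible.

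- **Rename.** In objective 3 and the secondary outcome, in both places where each appears, replace the apnea wording with *excessive daytime sleepiness (Epworth)*. Pre-specify the cut-off that defines a case for the odds ratio, or analyse the score as continuous. State that no conclusion about sleep apnea will be drawn. The cost is a change of wording and a narrower claim.
- **Keep the name and measure it.** Add interview items on breathing symptoms, such as habitual loud snoring, witnessed pauses in breathing and waking choking. If an attached form already contains such items, cite it. State the rule that combines them into the outcome, with the basis for that rule, and report Epworth separately. The cost is a few more questions in an interview already planned, plus the work of choosing and justifying the items.

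If interviews have already been done without such items, they cannot be reconstructed from Epworth scores, and renaming is the route left for those women.

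Showing the sleepiness result with and without the Beck score, which is already collected, is an optional sensitivity analysis under either route.

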### Aims and objectives

#### Primary:

1. To determine the prevalence of PCOS among women of reproductive age (a selected population (18 to 45)) in Trinidad.

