**TABLE 1. Screening laboratory evaluations\***

PCOS Inclusion/Exclusion labs	
•	TSH**
•	PRL**
•	17-OHP***
•	P4++
•	oGTT**

\* To be determined in local clinical lab (MDS Biochemistry Laboratory) in UWI, Trinidad.

\*\* All subjects.

\*\*\* For subjects with oligomenorrhea and/or hirsutism and/or PCOM only, who do not use Hormonal Contraception (HC).

++ For subjects with hirsutism and/or PCOM, who have apparently regular menstrual bleeding a day 22–24 progesterone (P4) level will be obtained.

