### ***Adverse Events (AE)***

An adverse event (AE) is defined as any unfavorable and unintended sign (including an abnormal laboratory finding), symptom, or disease temporally occurring during the course of the study, whether associated or not with the procedures performed during the study. AEs may include the following types of occurrences:

- Suspected adverse drug reactions.
- Other medical experiences, regardless of their relationship with the study procedures performed, such as injury, surgery, accidents, extensions of symptoms or apparently unrelated illnesses, and significant abnormalities in clinical laboratory values, psychological testing or physical examination findings.
- Reactions due to medication (e.g. solutions administrated for the OGTT and ACTH stimulation test) overdose, abuse, misuse, withdrawal, sensitivity or toxicity.

Investigators must systematically assess the severity of AEs according to the following definitions:

- ***Mild:*** The subject is aware of the event or symptom, but the event or symptom is easily tolerated.
- ***Moderate:*** The subject experiences sufficient discomfort to interfere with or reduce his or her usual level of activity.
- ***Severe:*** Significant impairment of functioning: the subject is unable to carry out usual activities and/or the subject's life is at risk from the event

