#### **Example AE & SAEs in proposed study:**

Overall, the likelihood of AEs and SAEs in this study is very small. Examples of possible AEs may include:

- Bruising at the site of blood drawing (mild AE)
- Flushing with the administration of ACTH-1-24 for acute ACTH stimulation test to exclude NCAH (mild AE).
- Discomfort with transvaginal ultrasound (mild AE).
- Emotional distress upon knowing of the diagnosis of PCOS (mild to moderate AE).

Since the protocol does not entail any intervention, it is very unlikely that any SAE will occur.

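### The 17-OH progesterone cut-off for NCAH is printed as two values 100-fold apart in the same unit, so a threshold used in deciding who counts as PCOS is wrong as written

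*Combined protocol and SAP*

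**What the plan says.** The rule is in the Study procedure section: "Study participants with elevated 17-OH progesterone > 2ng/dl (or 200 ng/dl) will have non-classical congenital adrenal hyperplasia (NCAH"). The sentence shortly before it gives the test its purpose: "Related or mimicking disorders will be excluded using history, physical examination, and serum TSH, prolactin and 17-OH progesterone".

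Table 1 of the screening laboratory section lists 17-OHP under the label "PCOS Inclusion/Exclusion labs". Its footnotes limit the test to women with oligomenorrhea, hirsutism or PCOM who do not use hormonal contraception, and name where it is run: "To be determined in local clinical lab (MDS Biochemistry Laboratory) in UWI, Trinidad". The table gives no cut-off, and neither do the selection criteria.

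The primary objective is "To determine the prevalence of PCOS among women of reproductive age" in Trinidad.

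A second test for NCAH appears only in the safety text. The Adverse Events section refers to "solutions administrated for the OGTT and ACTH stimulation test", and the list of example events refers to "administration of ACTH-1-24 for acute ACTH stimulation test to exclude NCAH".

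**The concern.** The sentence joins the two figures with *or*, as if they were equivalent, yet prints both in ng/dl. A reader who applies the text literally has two cut-offs and no means of choosing between them.

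This is a working threshold and not background. Of the three serum tests named for excluding mimicking disorders (TSH, prolactin, 17-OH progesterone), it is the only one with a numeric cut-off in the readable text. Hormone samples are to be assayed in batches during the study so that participants can be classified, so the number is needed while the study is running. A woman labelled as having NCAH has a mimicking disorder, and whether she counts as a PCOS case turns on that label.

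There is also a lesser wording point. The Study procedure sentence says that women above the cut-off have NCAH, whereas the safety text describes a stimulation test used to exclude it. A screening value followed by a stimulation test would explain both.

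**Working it through.** **Inputs.** First value: above 2 ng/dl. Second value: 200 ng/dl. Both come from the one sentence in Study procedure. Conversions: 1 dl = 100 ml, so 1 ng/ml = 100 ng/dl; also 1 ug/l = 100 ng/dl, 1 ug/dl = 1000 ng/dl, and 1 ng/l = 1 pg/ml = 0.1 ng/dl.

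**Step 1: try to reproduce the stated equivalence.** In the printed unit, 200 / 2 = 100. In ng/ml, 2 ng/dl = 0.02 ng/ml and 200 ng/dl = 2 ng/ml. The equivalence fails by a factor of exactly 100.

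**Step 2: see whether a change of unit on one figure would restore it.**

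| Unit tried | 2 in this unit, as ng/dl | Equals 200 ng/dl? | 200 in this unit, as ng/dl | Equals 2 ng/dl? |
|---|---|---|---|---|
| ng/dl (as printed) | 2 | no | 200 | no |
| ng/ml | 200 | yes | 20,000 | no |
| ug/l | 200 | yes | 20,000 | no |
| ug/dl | 2,000 | no | 200,000 | no |
| ng/l or pg/ml | 0.2 | no | 20 | no |

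The pair agrees only if the first figure carries a unit 100 times larger. That fits a misprint of the unit. It is arithmetic about the sentence and does not show which threshold the sponsor intends.

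**Step 3: where the two readings disagree.**

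| Result (ng/dl) | Cut-off above 2 | Cut-off above 200 |
|---|---|---|
| 2 or less | not NCAH | not NCAH |
| above 2, up to 200 | NCAH | not NCAH |
| above 200 | NCAH | NCAH |

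The band of disagreement is 200 - 2 = 198 ng/dl wide (above 0.02 and up to 2 ng/ml). Every woman above 200 is also above 2, so the lower figure can only add NCAH labels. If an NCAH label removes a woman from the PCOS count, that count can only stay the same or fall.

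**Step 4: who is affected.** Only the subset in the Table 1 footnote is tested. The four phenotypes in the secondary objectives are A (HA, OA and PCOM), B (HA and OA), C (HA and PCOM) and D (OA and PCOM). Each needs OA or PCOM, so the tested subset is broadly where PCOS cases arise. The overlap need not be complete, because oligomenorrhea is not identical to OA. The sample size was also set for women not using hormonal contraception.

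**Step 5: sample size.** 1.96² × 0.134 × 0.866 / 0.03² = 495.3, against the stated 495, and 495 / 0.5 = 990 as stated. The cut-off does not enter this formula.

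**The case against.** The strongest reply is that this is a one-character misprint with an inferable intent. The bracketed *or* reads as one threshold written two ways, only a change of unit on the first figure makes the pair agree, and nothing suggests that staff hold two competing cut-offs. All of that is fair. It makes the matter a correction and not a design flaw. It does not remove the need for the correction: a classification rule has to be usable as printed, and the text does not itself say which figure or unit is at fault.

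A second reply is that the operative rule may be elsewhere. Classification follows a diagnostic tree in Figure 1, and Study procedure ends by announcing "A summary of initial and follow-up procedures"; neither can be seen here. Either could state a single value or set out the stimulation test step. That limits what can be said about the rule used in practice, but the sentence would still contradict itself. It also cannot be confirmed here whether the slip is in the source or arose in reading the PDF.

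A third reply is that impact is limited. The test is not done in everyone, and the case report form has a laboratory section, so labels could be reapplied if the numeric results are kept. Both points stand as limits on the harm. The restriction on testing removes little, because the women tested are the likely PCOS candidates.

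**Conclusion.** The concern holds. As printed, the cut-off is two numbers 100-fold apart in one unit, so at least one number or unit must be wrong, and no readable section resolves it. The two readings give opposite labels for any tested woman with a result above 2 and up to 200 ng/dl.

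Confidence in the printed contradiction is high. The link to the primary outcome rests on the plan's own use of 17-OH progesterone to exclude mimicking disorders and on Table 1. The size of any effect on prevalence is unknown, and no estimate is offered. The difference between the NCAH sentence and the safety text is only a wording check, since the unseen figure or summary may reconcile them.

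This should be corrected, but it does not call the design into question.

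**What to change.** Reconcile the two printed values and state the threshold once, as one number in the unit reported by the laboratory that runs the assay; Table 1 assigns 17-OHP to the local clinical laboratory. Do this before any woman is classified.

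In the same edit, check that the wording on who has NCAH agrees with the stimulation test mentioned in the adverse event sections, with Figure 1 and with the procedure summary. Which value and which test apply is for the sponsor to settle.

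The cost is one corrected sentence and a short cross-check. The unit correction itself changes neither the sample size nor the data collected.
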